7.0 Research Plan and Procedures

7.1 This new consolidated section requests information about:

- Hypothesis
- Aims
- Study Design
- Background and Significance
- Preliminary Studies
- Procedures
- Statistical Methods
- References

Later sections include:

- Drugs and Devices
- Sample Size, Eligibility, and Subjects
- Recruitment and Consent
- Risks and Benefits
- Data and Safety Monitoring Plan
- Confidentiality, Privacy and Security
- Financial Considerations
- Qualifications of Personnel
- Other Approval and Registrations

7.2 HYPOTHESIS: Describe the hypothesis or what the study hopes to prove **(Help Text updated 9/13):**

We propose that patients with Polycystic Ovary Syndrome (PCOS) on a continuous 6 month active oral contraceptive (OCP) preparation (no placebo pills for 6 months straight) will have improved Testosterone suppression as compared to patients taking cyclical (monthly) OCPs, who may have rebound ovarian function during days 21-28 of their menstrual cycle when receiving sugar pills. With continuous OCP use we also hypothesize that patients will have improved clinical findings of hyperandrogenism (acne and hirsutism) compared to cyclic OCP users.

7.3 AIMS: List the specific aims:

1. To conduct a pilot feasibility study observing the use of 2 formulations of an OCP (continuous 168 day active hormone pills vs. cyclical 21 day active/7day placebo pill packs) in patients with Polycystic Ovary Syndrome (PCOS).
2. To determine the effect of 6 months of continuous (168 days of active hormone pills) vs. cyclical (21 day active and 7 day placebo pills) OCP therapy on biochemical findings of hyperandrogenism (Testosterone levels and free androgen index).
3. To determine the effect of 6 months of continuous (168 days of active hormone pills) vs. cyclical (21 day active/7 day placebo pills) OCP therapy on cutaneous findings of hyperandrogenism (male pattern hair growth also known as hirsutism and acne).
4. To determine the effect of 6 months of continuous (168 days of active hormone pills) vs. cyclical (21 day active/7 day placebo pills) OCP therapy on self reported symptoms of anxiety and /or depression as collected from validated questionnaires.

7.4 DESIGN: Briefly describe the study design (e.g., observational, interventional, randomized, placebo-controlled, blinded, cross-over, cross-sectional, longitudinal, pharmacokinetic, etc.):

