At 3 months into therapy, participants will come back to the PCOS clinic for routine care follow up and be seen by a Reproductive Endocrinology and Fertility specialist. This visit is considered routine and not specific to the study. However, during this visit a study investigator will also touch base briefly with the participants to see how they are doing. Four online surveys (through REDCap) will also be sent to participants that addresses if they have missed any doses of their medication, assess their quality of life, acne changes, screen for anxiety and depression. Patients will be asked to complete the BDI-II survey on their clinic day so that it can be evaluated by the study team immediately in the event that there are concerns for suicidal risk. In addition, participants will once again get blood work at their visit (including total Testosterone, SHBG, estradiol, LH, FSH) but will also go to their local lab (covered by their insurance) for additional routine labs including a fasting lipid panel, fasting serum glucose, insulin, and HbA1c. These labs are routinely done with follow up regardless of being in the study and should therefore be covered by each participant's insurance. Once again, the cyclical group should be on placebo/sugar pills at the time of blood draw and the continuous group on active hormone pills.

At 6 months into therapy, participants will come in for a study visit (this is not considered routine care) in which they will have their vitals taken, a physical exam that includes a re-evaluation of their mFG score, and an in-clinic pelvic ultrasound to assess ovarian volume and follicle counts performed by a Reproductive Endocrinology and Infertility specialist. They will also be emailed 5 post-study surveys through REDCap, that includes a quality of life questionnaire for PCOS, acne and hirsutism, as well as anxiety and depression screening, and includes questions regarding any missed doses of their medication. Patients will again be asked to complete the BDI-II survey on their clinic day so that it can be evaluated by the study team immediately in the event that there are concerns for suicidal risk. Lastly, participants will again have blood work drawn in the clinic (total Testosterone, SHBG, estradiol, LH, FSH). These labs are not considered standard of care and will be paid for by the study team.

Participants may also be called emailed reminders for follow up at least 2-3 times during the 6 month period.

CCOUP Study Timeline

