	Screening	Enrollment	1 month	3 months	(routine)
Questionnaires					
REDCap PCOS Multidisciplinary PCOS Clinic Pre-clinic Surveys (routine)	x				
REDCap Baseline Questionnaire		x			
REDCap 3 Month Follow Up Questionnaire /PCOS QOL				x	
REDCap 3 Month GAD-7 Questionnaire				x	
REDCap 3 month BDI-II Survey				x	
REDCap 3 Month Follow Up - Acne QOL Assessment				x	
REDCap 6 Month Follow Up Questionnaire /PCOS QOL					
REDCap 6 Month GAD-7 Questionnaire 2					
REDCap 6 Mond BDI-II Survey 2					
REDCap 6 Month Follow Up Questionnaire - Acne QOL Assessment					
REDCap 6 Month Follow Up Questionnaire - Hirsutism QOL Assessment					
Study Visits/Procedures					
Dermatologic Exam (mFG scoring)		x			
Pelvic Ultrasound		x			
Blood Work - Location	Patient's local lab - insurance covered	PCOS Clinic - study covers	PCOS Clinic - study covers	PCOS Clinic - study covers	Patient's local lab - insurance covered
Total Testosterone	x (routine)	*	†	†	
Free Testosterone	x (routine)	**			
Sex Hormone Binding Globulin	x (routine)	*	†	†	
LH	x (routine)	**	×		x
FSH	x (routine)	*	×		x
Estradiol	x (routine)	**	×		x
Fasting Lipid Panel	x (routine)	**			x
HbA1c	x (routine)	**			x
Fasting serum glucose	x (routine)	**			x
Insulin	x (routine)	**	†	†	
Email Reminders		x			x
* if initial screening blood work done at the patient's outside lab is obtained >2 months from start of study, these select labs will be sent from the PCOS clinic to the University of Virginia, Center for Endocrinology and Metabolism to establish accurate baseline values.					
** If the patient is a return patient to the clinic looking to reestablish care and participate with the study, all labs will be sent from the PCOS clinic to the University of Virginia, Center for Endocrinology and Metabolism to establish accurate baseline values.					
† indicates the select labs that will be sent from the PCOS clinic (where it is drawn) to the University of Virginia, Center for Endocrinology and Metabolism to establish accurate baseline values.					
Please refer to the attached study document "CCOUP Study Timeline" for the full procedure table.					

7.11 STANDARD CLINICAL PRACTICE: To what extent, if any, do the planned research procedures differ

from the care that people would otherwise receive at this institution or the study site if not being done locally:

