If the goal of therapy is management of hyperandrogenism and menstrual dysfunction, combined oral contraceptive pills (OCPs) are the mainstay of treatment based on *Endocrine Society* guidelines of PCOS. While there is no standard of care established regarding which combined OCP formulation and length of active pills that should be used in the treatment of women with PCOS, the mainstay of therapy has largely been monthly pill packs (21 days of active and 7 days of placebo pills) though continuous 3-6 month formulations have been used, with a 3rd or 4th generation progestin that provides some anti-androgen effect. Therapy with OCPs are individualized to each patient given the multitude of different formulations and their side effect profiles. In patients who have concerns for hirsutism an additional medication such as Spironolactone is often added to therapy. However, studies have shown that 4th generation progestins such as Drospirenone have a component of Spironolactone effect, limiting the need for dual therapy.

Comparatively, this study will use standard clinical practice guidelines in treating participants with an OCP that has a 4th generation progestin, Drospirenone. In addition, it is also standard clinical practice that patients seen at the PCOS Multidisciplinary clinic who are started on OCP therapy are followed up in 3 months for both a clinic visit and typically get routine blood work at this time as well.

Procedures that differ from the standard clinical practice in this study include: repeat blood work at 1 month and 6 months into OCP therapy, repeat pelvic ultrasound to assess ovarian volume and follicle counts at 6 months of therapy, and lastly a repeat modified Ferriman-Gallwey Hirsutism scoring done with a physical exam at the 6 month follow up.

7.12 INSTRUMENTS: List all questionnaires, surveys, interview, or focus group guides that will be used for this study:

	Screening	Enrollment	1 month	3 months	(routine)
Questionnaires					
REDCap PCOS Multidisciplinary PCOS Clinic Pre-clinic Surveys (routine)	x				
REDCap Baseline Questionnaire		x			
REDCap 3 Month Follow Up Questionnaire /PCOS QOL				x	
REDCap 3 Month GAD-7 Questionnaire				x	
REDCap 3 Month BDI-II Survey				x	
REDCap 3 Month Follow Up - Acne QOL Assessment				x	
REDCap 6 Month Follow Up Questionnaire /PCOS QOL					
REDCap 6 Month GAD-7 Questionnaire 2					
REDCap 6 Month BDI-II Survey 2					
REDCap 6 Month Follow Up Questionnaire - Acne QOL Assessment					

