7.18 SPECIMENS SENT OUTSIDE UCSF - IDENTIFIABILITY: Will direct identifiers be associated with specimens or shared with other researchers and/or outside entities:

Yes
 No
 N/A - Specimens will not be shared with others

7.19 * FUTURE SPECIMEN USE: Will any specimens or portions of specimens be retained after the study is over for possible use in future research studies: (REQUIRED)

Yes No

7.21 * CLINICAL FOLLOW-UP DATA: Will clinical follow-up data be linked to specimens (i.e., will medical record information continue to be abstracted after the specimen is collected): (REQUIRED)

Yes No

Provide duration of follow-up or 'indefinitely':

7.26 STATISTICAL METHODS: Briefly summarize the methods and types of analyses that will be performed:

The means and standard deviation will be calculated for each of the blood tests within each treatment group and compared at the different time points to baseline measures. Additionally we will likely use a two sample t-test to estimate the difference in the mean Testosterone levels between the two treatment groups over the 6 month period. Analysis of covariance models, adjusted for the baseline measurement, will also likely be used to compare the treatment groups for metabolic parameters. Chi-Square analyses will be used to compare the treatment groups for reported anxiety and depression as analyzed categorically.

7.27 REFERENCES: List only the 5-10 most relevant references (a separate bibliography can be attached for reference purposes if this study involves novel approaches, agents, or an emerging technology that the IRB may not be familiar with):

3. The Rotterdam ESHRE/ASRM-Sponsored PCOS Consensus Workshop Group 2004 Revised 2003 consensus on diagnostic criteria and long-term health risks related to polycystic ovary syndrome. *Fertil Steril* 81:19-25.

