Trial Stopping Rules: In the event that a rare but serious side effect such as a thromboembolism or hepatocellular carcinoma occurs within multiple subjects within a study group, the PI will investigate this adverse event (AE) to determine the safety of continuing the trial further. As this pilot study will be recruiting individuals over a long period of time, the PI and investigators will meet to discuss on an on-going basis patient AE to determine if there is a need to stopping the trial due to patient safety concerns.

A suicidal ideation and depression protocol has also been set in place in case a patient is found to have answered Question 9 of the BDI-II surveys with a score greater than zero or a total score over 19. The protocol details specific steps that need to be taken immediately including contacting [name] and following up with the patient immediately. Details of the protocol have been attached to this application as a separate document.

14.3 * DATA AND SAFETY MONITORING BOARD (DSMB): Will a Data and Safety Monitoring Board (DSMB) be established: (REQUIRED)

Yes
 No

Guidelines

A Data and Safety Monitoring Board (DSMB) or Data Monitoring Committee (DMC) is a formal, independent committee that is specifically established to conduct interim monitoring, oversight and analysis of study information and data to assure the continuing safety, efficacy, appropriateness, relevance,

and integrity of the study.

The UCSF IRB reserves the right to request a DSMB/DMC for any study. However, the following are factors that the IRB will consider when making this determination:

- There is a significant likelihood of a serious adverse event to subjects
- The study is conducted at multiple sites and the level of risk is greater than minimal
- The study generates data that are blinded or randomized
- The study involves a large number of patients randomized to one of two or more interventions
- A study for which the performance of an interim analysis is crucial for the protection of the subjects
- First use in humans
- First use in children
- The study involves gene transfer, stem cell therapy, or other novel interventions for which long-term outcome data are not known or available

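### For Aim 4, section 7.26 names only a chi-square on undefined anxiety and depression categories, although GAD-7 and BDI-II totals are collected at months 3 and 6 and carry more information if scores shift broadly

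*Combined protocol and SAP*

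**What the plan says.** Aim 4 (section 7.3) is the effect of the two regimens on "self reported symptoms of anxiety and /or depression as collected from validated questionnaires". Its only named analysis is in section 7.26: "Chi-Square analyses will be used to compare the treatment groups for reported anxiety and depression as analyzed categorically".

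The other methods in 7.26 are tied to other outcomes. Means and SDs are for the blood tests, the two-sample t-test is for testosterone, and the baseline-adjusted model is for metabolic measures: "Analysis of covariance models, adjusted for the baseline measurement, will also likely be used to compare the treatment groups for metabolic parameters".

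Both scales are collected twice. Section 7.10 says the month-3 surveys will "assess their quality of life, acne changes, screen for anxiety and depression" and describes the same screening again at month 6. The instrument list in 7.12 names both forms at month 3, and at month 6 it has "REDCap 6 Month GAD-7 Questionnaire 2" and "REDCap 6 Month BDI-II Survey 2". Section 15.5 also counts two depression assessments.

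The only BDI-II threshold is in section 14.2. It triggers the suicidal-ideation protocol when a patient has "answered Question 9 of the BDI-II surveys with a score greater than zero or a total score over 19". Nothing links it to the analysis, and no GAD-7 threshold appears anywhere. A "REDCap Baseline Questionnaire" is listed at enrolment in the 7.10 timeline, but its contents are not shown.

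**The concern.** GAD-7 and BDI-II both produce a total score. Reducing a total to categories treats everyone within a category as equal, and in a study of 60 that loss is hard to afford. It is also avoidable, because the totals will already be in the database.

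Two further things are at stake. A pilot should supply planning figures for a later trial, and a chi-square alone supplies neither a mean difference nor an SD for these scales. And with two scales, two visits and no stated cut-off, the choice of category and visit could be made after the data are seen.

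**Working it through.** **Inputs.** From the documents: 30 per arm (9.1, 9.3), 1:1 allocation (7.4), both scales at months 3 and 6 (7.10, 7.12). The plan states no significance level, power, effect size, SD, share above a cut or dropout, so it has no figure to reproduce. Assumed here: two-sided 5%; 15–50% of the reference arm above the cut; no losses unless stated.

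**Step 1: information kept by a two-way cut.** For a normal score with share q above the cut at z, relative efficiency is φ(z)² / [q(1−q)].

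- q = 0.50: 0.3989² / 0.25 = 0.637
- q = 0.25: 0.3178² / 0.1875 = 0.539
- q = 0.15: 0.2332² / 0.1275 = 0.426

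**Step 2: total scores.** For a two-sample t-test with 30 per arm, the non-centrality is d√(30/2), with 58 degrees of freedom. At d = 0.736 this is 2.85 and power is 80%. The 95% CI half-width is 2.002 × √(2/30) = 0.52 SD.

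**Step 3: chi-square on the same shift.** Each shift is converted to two proportions, and power is found by exact enumeration of the uncorrected test. Example: with 25% above the cut (z = 0.674), a fall of 0.736 SD leaves P(Z > 1.410) = 7.9%, and power is 44.5%. At 0.736 SD:

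| Reference share above cut | Share rises | Share falls |
|---|---|---|
| 15% | 53.8% | 33.4% |
| 20% | 56.9% | 40.4% |
| 25% | 59.3% | 44.5% |
| 50% | 58.4% | 58.4% |

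Over the same shares and both directions:

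| True difference | Means | Chi-square |
|---|---|---|
| 0.74 SD | 80% | 33–59% |
| 0.5 SD | 48% | 21–33% |
| 0.3 SD | 21% | 11–15% |

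If 15% is the reference share and the other arm has no one above the cut, significance needs at least 4 of 30, which has probability 0.678. So a fall from 15% cannot reach 80% power at this size.

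**Step 4: sensitivity.**

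- 24 per arm analysed (assumed 20% loss): means have 80% power at 0.83 SD, the chi-square 28–62%.
- Unordered chi-square on three or four categories, 30 per arm, 0.736 SD: 28–59%.
- Skewed integer scores (gamma shapes 1, 2 and 4) with the t-test at about 80%: chi-square 41–64%.
- Averaging months 3 and 6 lowers the difference detectable with 80% power from 0.736 to 0.736 × √[(1+ρ)/2], which is 0.64 SD at ρ = 0.5 and 0.70 SD at ρ = 0.8 (ρ is the between-visit correlation; same effect at both visits, none missing).

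**Step 5: an effect confined to a minority.** Scores were simulated as rounded gamma values (shape 1.5, scale 4), 30 per arm, with 25% of one arm raised by 15 points. The t-test has 57% power. The chi-square on scores above the cut has about 64% at a cut of 13 and 72% at 15, but only about 41% at 9 and 45% at 19. Here the ordering depends on the cut.

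**The case against.** The best counter-argument is Step 5. Section 7.10 describes these forms as screening, so the share of women above a threshold is a defensible quantity, and if only a minority are affected a well-placed cut can beat the mean. That stands: it limits the precision claim to broad shifts and justifies keeping the categories. It does not rescue the present wording, because the advantage needs a suitable cut and 7.26 names none.

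Second, the arms take the same pill and differ only in the placebo week, so nothing in the documents suggests an effect as large as 0.74 SD. Also correct. At 0.3 SD neither analysis is informative on its own, and the practical gain is then mainly an estimate with an interval and an SD.

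Third, 7.26 is a form field asking for a brief summary, and Aim 4 is the last of four aims in a pilot. Naming a test for the categorical analysis does not forbid score summaries. That is fair and limits the weight of the point, but the section did choose a method for this aim and left the scores out.

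Two stronger readings are tempting. A reader might infer that the lack of baseline adjustment is itself a fault. The documents do not support this: the contents of the Baseline Questionnaire and of the pre-clinic psychological assessment (11.2) are not shown, so it cannot be told whether baseline scores exist. A reader might also infer an inflated false-positive rate. Reporting the best of two visits and three cuts on one scale would raise 5% to 20–22% in simulation, but nothing in the documents proposes three cuts or best-of reporting. That figure is a worst case of leaving the choice open and does not describe the plan.

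**Conclusion.** The point holds in qualified form. For Aim 4 the plan names only a categorical test with no cut-off or visit, while total scores on both scales will exist at two visits. If scores shift broadly, the two-way cut discards roughly 36–57% of the information, and at 0.74 SD power falls from 80% to 33–59%. These sizes rest on assumed distributions, shares above the cut, significance level and effect sizes; the direction was the same in every broad-shift scenario run, skewed scores included. It is not universal, as Step 5 shows.

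Randomisation keeps either between-arm comparison unbiased, and low power is expected at this size. A reader might go on to infer bias or an error in the target of 60; the documents support neither. This is an inexpensive improvement to an exploratory aim.

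**What to change.** In section 7.26:

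1. Compare GAD-7 and BDI-II total scores between arms at one named main time point, as a mean difference with 95% CI, or with a repeated-measures model over months 3 and 6. Report the SDs.
2. Keep the categorical comparison as secondary, with cut-offs, number of categories and visit fixed before the data are seen. State whether the section 14.2 safety threshold has any role in the analysis.
3. State whether the Baseline Questionnaire or pre-clinic survey already contains these scales. Adjust for baseline only if it does; otherwise leave the comparison unadjusted.

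The cost is a few sentences and a little more analysis work, with no new data, visits or participant burden. The trade-off is that the category comparison becomes secondary.

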8.0 Drugs and Devices

8.1 * DRUGS AND/OR BIOLOGICS: Are you **STUDYING** any drugs and/or biologics that are either approved or unapproved: **(REQUIRED)**

Yes No

8.2 LIST THE DRUGS OR BIOLOGICS: List the drugs or biologics that will be studied. In the drug details screen you will be asked questions such as:

- Whether the drug or biologic is FDA approved
- If the drug or biologic will be provided at no cost
- If an IND is necessary, the IND number, and who holds the IND
- If the drug or biologic is FDA approved and an IND is not required, the rationale for the decision
- If the **Investigational Drug Service (IDS)** is dispensing the drug or biologic (required unless a **waiver** is obtained from the IDS)

Please see the **UCSF IRB website** for more details about the use of drugs and biologics in research, including the **IND Decision Worksheet**. Verification of IND numbers: If the sponsor's protocol does not list the IND number, you must submit documentation from the sponsor or FDA identifying the IND number for this study. Attach this documentation in the Other Study Documents section of the Initial Review Submission Packet. **If you have any correspondence from the FDA or sponsor regarding this drug or biologic, please attach it to the application.**

View Details	Drug Name	FDA Approved	A new drug or a new use of an already approved drug:	IND Number
	Trade Drug Name: YASMIN Generic Drug Name: DROSPIRENONE; ETHINYLP	Yes	No	

Name: ESTRADIOL
**Investigational
Drug Name:**

Trade Drug Name:	YASMIN
Generic Drug Name:	DROSPIRENONE; ETHINYL ESTRADIOL
Investigational Drug Name:	
Identify the name of the manufacturer or source of investigational drug/biologic:	Bayer HealthCare Pharmaceuticals Inc.
Is the drug supplied at no cost?	No
Is the Drug FDA Approved:	Yes
Is this a new drug or a new use of an already approved drug	No
Is an IND necessary	No
IND Number	
Who holds the IND:	N/A
IND details:	
If FDA Approved and an IND is not required, Please provide a rationale for exemption:	
Are you currently using this IND in another research project?	No
If yes, list the IRB Number(s):	
Will the investigational pharmacy be dispensing?	No
If the source is not a FDA licensed facility, provide details regarding the purity, quality, stability and sterility of the investigational drug/biologic:	

8.3 * MEDICAL DEVICES: Are you **STUDYING any medical devices, in vitro diagnostics, or assays that are either approved or unapproved: **(REQUIRED)****

Yes No

8.6 * Is this an expanded access or compassionate use protocol, meaning the primary purpose is to diagnose, monitor or treat a patient's condition, rather than the collection of safety and efficacy data of the experimental agent: **(REQUIRED)**

Yes No

